POM, an analog of thalidomide, is an immunomodulatory agent with antineoplastic activity. In *in vitro* cellular assays, POM inhibits proliferation and induces apoptosis of hematopoietic tumor cells. Additionally, POM has been demonstrated to inhibit the proliferation of lenalidomide-resistant MM cell lines and synergizes with DEX in both lenalidomide-sensitive and lenalidomide-resistant cell lines to induce tumor cell apoptosis. POM has also been shown to enhance T cell- and natural killer cell-mediated immunity and inhibit production of pro-inflammatory cytokines (e.g., tumor necrosis factor-α and IL-6) by monocytes. POM is indicated for patients with MM who have received at least 2 prior therapies including lenalidomide and bortezomib and have demonstrated disease progression on or within 60 days of completion of the last therapy.

POM may be taken PO with water. Capsules should not be broken, chewed or opened. POM should be taken without food (at least 2 hours before or 2 hours after a meal).

POM will be commercially available.

DEXAMETHASONE

DEX, a high-potency corticosteroid, has known activity against MM and other (predominantly lymphoid) hematologic malignancies.

DEX will be commercially available. Tablets will be taken PO.

Study Design

This study is a phase 1/2 multi center, open label study of SL-401 in combination with standard doses of POM and DEX. The study will be conducted as a modified Fibonacci 3 + 3 dose escalation design to determine the MTD of SL-401 in combination with standard doses of POM and DEX. The study will be conducted in 2 Phases. Each evaluated SL-401 dose level will also incorporate an initial "Run-in Cycle" of single agent SL-401 in at least 3 patients; following the Run-in Cycle, patients who have not experienced a DLT will receive combination SL-401/POM/DEX. All patients in phase 2 will initiate therapy with the combination of SL-401/POM/DEX at the MTD or maximum tested dose established in phase 1.

Phase 1

Run-In Cycle: SL-401 will be administered as single agent during a Run-in Cycle. Upon completion of the Run-in Cycle patients will be evaluated for safety and response.

- Patients who do not experience a DLT during the Run-in Cycle will have POM/DEX added to their regimen at the assigned cohort dose.
- Patients who experience a DLT during the Run-in Cycle will be discontinued from study.

Table 1: Dose Levels to be Tested

	DLT EV	ALUTION PERIOD = R	UN-IN CYCLE AND CY	CLE 1
	()	Combination therapy Cycle 1 - 6		

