The study duration for an individual patient will include a screening period for inclusion of up to 21 days, the treatment period may continue for up to 6 cycles of combination therapy or until disease progression, unacceptable adverse reaction or other reason for discontinuation. The administration of additional cycles of SL-401 > 6 cycles (not including the Run-in Cycle if received) must be discussed with the Medical Monitor at which time the individual patient's potential risk/benefit of further treatment will be assessed. After study drug discontinuation an end of treatment (EOT) visit will be done at approximately 30 days to assess safety. Patients who discontinue treatment for reasons other than progression of disease will be followed monthly until progression or initiation of subsequent therapy. Following progression, either on or off therapy patients will be followed for overall survival every 3 months for a maximum of 1 year, whichever comes first.

Overall Study Duration:

The dose escalation stage (phase 1) will require approximately 6 to 18 patients to evaluate 3 dose levels of SL-401/POM/DEX. In phase 2, 14 additional patients will be treated (20 total patients) at the MTD or maximum tested dose. Total study duration is expected to be approximately 24 months. Patient enrollment is expected to occur over a 12-month period, with follow-up continuing until assessments of the primary and critical secondary objectives are completed for all treated patients.

2 Abbreviations and Definitions

Abbreviation	Definition
AE	Adverse Event
ALL	Acute Lymphoid Leukemia
ALT	Alanine Transaminase
AML	Acute Myeloid Leukemia
ANC	Absolute Neutrophil Count
AP	Alkaline Phosphatase
AST	Aspartate Transaminase
BM	Bone Marrow
BMSC	Bone Marrow Stromal Cell
BP	Blood Pressure
BPDCN	Blastic Plasmacytoid Dendritic Cell Neoplasm
BSA	Body Surface Area
BUN	Blood Urea Nitrogen
CBC	Complete Blood Count
CFR	Code of Federal Regulations
CML	Chronic Myeloid Leukemia
CPK	Creatine Phosphokinase
CR	Complete Response
CSC	Cancer Stem Cell
CTCAE	Common Terminology Criteria for Adverse Events
DEX	Dexamethasone
DLT	Dose-Limiting Toxicity
DOR	Duration of Response
DP	Drug Product
DSRC	Data Safety Review Committee
DT	Diphtheria Toxin
ECG	Electrocardiogram
ЕСНО	Echocardiogram
ECM	Extracellular matrix
ECM	Extracellular matrix

Abbreviation	Definition
ECOG	Eastern Cooperative Oncology Group
eCRF	Electronic Case Report Form
EDC	Electronic Data Capture
EDTA	Ethylenediaminetetraacetic Acid

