7.9.2 Procedures and Follow-up after Treatment Discontinuation

The evaluation during which the Investigator determines that SL-401 or SL-401/POM/DEX will be discontinued should be considered the EOT Evaluation; all tests and procedures for the EOT Evaluation are listed in Table 13. In addition, patients should be followed for a minimum of 30 days after the last dose of SL-401 or SL-401/POM/DEX for assessment of AEs (including potential new AEs and potential change/resolution of existing AEs).

Patients who discontinue therapy for reasons other than progression will be followed every month until progression of disease or initiation of subsequent therapy. Disease assessments should continue to be performed as described in Table 13, until there is evidence of relapsed or progressive disease in the judgment of the Investigator. Following progression, either on or off therapy, patients will be followed for survival every 3 months for up to 1 year.

If the patient discontinues SL-401 treatment and also withdraws consent for collection of future information, no further evaluations should be performed and no additional data should be collected as part of the study. The Sponsor will only retain and use any data collected before withdrawal of consent.

Consult Section 6.4 for recommendations concerning ongoing follow-up of patients alive with or without evidence of disease progression at the time of Study Completion/assessment of primary and critical secondary endpoints.

8 Study Procedures

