9.7 Follow-Up

Patients who discontinue therapy for reasons other than MM progression will be followed for disease response every month until progression of disease or initiation of subsequent therapy. Patients who have discontinued study therapy and have had MM progression should be contacted approximately every 3 months (telephone contact is permitted) to assess survival status for up to one year; patients who discontinue therapy for reasons other than disease progression and are no longer willing to follow-up for evaluation of disease progression should also be contacted for survival status whenever feasible.

Table 13: Schedule of Events

	Screening/ Baseline	Run in Cycle Cycle is 28 days																	
Evaluation	D-21 to -1	D 1	D 2	D 3	D 4	D 5	D 8	D 15	D 22	D 1	D 2	D 3	D 4	D 5	D 8	D 15	D 22	EOT	F/Uw
Informed Consent & Pomalyst REMS ^a	х																		
Entry Criteria Review	Х											,							
Medical and Myeloma History	x																		
Physical Examination ^c	X	X	Х	Х	Х	Х	X	Х	Х	х	X	Х	Х	Х	Х	X	Х	X	
Performance Status (ECOG)	х	x								х								x	
Height (Baseline only) / Weight	х	x	х	х	х	х	x	х	х	х	х	х	х	х	х	х	х	х	
Vital Signs (HR, Temperature, RR, $\mathrm{BP})^{\mathrm{d}}$	x	X	x	х	х	х	x	x		х	х	x	x	x	x	x		x	
ECG	X									х								х	
ECHO/MUGA	х								77										
Pregnancy testing [FCBP) and counseling *	х								Xe	х					Xe	Xe	Xe	х	
Hematology	X	x	x	х	х	х	x	x	x	Xf	x	х	х	x	х	x	х	x	
Serum Chemistry®	X	X	X	Х	х	X	X	X	X	Х	х	Х	X	Х	X	X	Х	X	
PT / INR aPTT	х									х								x	
Urinalysis h	Х	X								х								х	
Plasmacytoma Evaluation ⁱ	x									Xi								x	As needed
Skeletal Survey j	X																		As needed
Bone Marrow Aspiration and biopsy ^k	х									Xk								х	
Peripheral blood for correlative studies ¹	x									Xl								x	

	Screening/ Baseline				Run ir ycle is					Cycles 1 - 6 ⁿ Each Cycle is 28 days									
Evaluation	D-21 to -1	D 1	D 2	D 3	D 4	D 5	D 8	D 15	D 22	D 1	D 2	D 3	D 4	D 5	D 8	D 15	D 22	ЕОТ	F/U ^w
Myeloma-specific Laboratory Tests ^m	x	х								х								х	As needed
PK (SL-401) ⁿ		Х				х				X C2				X C2				x	
Immunogenicity (SL-401)°		x				х				х								x	
SL-401 Pre-medication ^p		x	x	x	x	x				x	x	x	x	x					
SL-401 Administration ^q		х	X	Х	Х	Х				Х	X	х	х	Х					
Pomalidomide ^r										Days 1 - 21									
Dexamethasone										x					x	x	x		
Adverse Event monitoring ⁶	x		← X →							x									
Prior/Concomitant Medication ^t	x			← X →							x								

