11.3 Determination of Sample Size

The primary objectives of phase 1 of the study are to evaluate the safety of Sl-401 as a single agent in an initial Run-in Cycle, to determine the MTD or the maximum tested dose where multiple DLTs are not observed and to further characterize the safety profile of SL-401/POM//DEX at the MTD. Based on such a recommended dose for phase 2 studies will be defined. A maximum of 3 dose levels (7, 9, and 12 μg/kg/day) is anticipated and thus the total number of patient for this stage ranges from 6 to 18. The anticipated same size is sufficient to evaluate these objectives. A secondary objective is to characterize the anti-tumor activity of SL-401/POM/DEX in terms of ORR, CBR, PFS and PFS-6. During phase 2, if approximately 14 patients are enrolled at the recommended phase 2 dose as defined in phase 1 over 12 months and follow-up continues for 12 months after the last enrolled patient, the total of 20 patients treated at this dose has approximately 75% power with a 1-sided type I error rate of 5% to reject the null hypothesis that the PFS-6 is <40% if the true rate is 60%.

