11.6 Analyses of Efficacy Data

The study will preliminary evaluate the activity of the SL-410/POM/DEX regimen. Secondary efficacy endpoints will include: PFS and PFS-6; ORR (CR + VGPR + PR) and clinical benefit rate (CR + VGPR + PR + MR) based on IMWG defined response criteria, as well as DOR; and OS. Response rates and depth of response will be calculated as the percent of evaluable patients that have confirmed sCR/CR/VGPR or PR, and exact 95% confidence intervals will be calculated for these estimates. Time to response, duration of response, and survival will be estimated using the product-limit method of Kaplan and Meier. For subgroups of patients defined by disease and line of therapy, exact 1-sided 95% confidence intervals will be calculated

for ORR and clinical benefit rates, and the distributions for duration of response, PFS, PFS6, and OS will be estimated by Kaplan-Meier methodology.

Efficacy assessment parameters will include:

- M-protein determination using both of the following procedures:
 - SPEP and serum protein immunofixation with quantitative immunoglobulins; and
 - UPEP and urine protein immunofixation (all using the same 24-hour urine collection)
- Serum FLC
- BM to quantify percent MM cell involvement
- Plasmacytoma evaluation: PET/CT scan or MRI and or physical exam as clinically indicated
- Skeletal survey
- Serum β2 microglobulin
- Cytogenetic analysis/FISH from BM aspirate

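### Survival contact runs only from progression to one year after it, with none scheduled after new therapy, so OS censoring depends on prognosis and late Kaplan-Meier OS may be biased in either direction

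*Protocol*

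**What the plan says.** - **Survival contact.** The synopsis (Duration of Study Period) says: "Following progression, either on or off therapy patients will be followed for overall survival every 3 months for a maximum of 1 year". Section 7.9.2 has the same rule: "Following progression, either on or off therapy, patients will be followed for survival every 3 months for up to 1 year". Sections 6.4 and 9.7 and Table 13 footnote w agree. The synopsis sentence then closes with a whichever-comes-first phrase, although it names only one limit.
- **Patients off treatment without progression.** Section 7.9.2: "Patients who discontinue therapy for reasons other than progression will be followed every month until progression of disease or initiation of subsequent therapy". The synopsis says that they "will be followed monthly until progression or initiation of subsequent therapy". The only other survival contact for patients without progression is in Section 9.7 and footnote w. It covers those who "are no longer willing to follow-up for evaluation of disease progression should also be contacted for survival status whenever feasible", and no interval is given.
- **Run-in DLT.** The synopsis and Section 6.2.1 say: "Patients who experience a DLT during the Run-in Cycle will be discontinued from study".
- **Analysis.** OS is a secondary objective (Section 4.2). Under Section 11.6, "survival will be estimated using the product-limit method of Kaplan and Meier". The sample-size text in Section 11.3 assumes enrolment over 12 months and that "follow-up continues for 12 months after the last enrolled patient". Section 6.3 expects a total duration of about 24 months.

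**The concern.** Kaplan-Meier lets the patients still under observation stand in for those censored. That is sound when censoring is unrelated to the risk of death, as with a common calendar cut-off. Here each patient's last survival contact is set by that patient's own progression date plus one year. After month 12 the early progressors leave the risk set first, while patients who progressed late or not at all stay in it. A patient who stops for toxicity and starts another treatment before progression leaves the monthly schedule and has no scheduled survival contact afterwards.

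At stake is the late part of the OS curve and the deaths behind it, in a study with about 20 patients at the phase 2 dose. The stated rule itself creates the problem, so a statistical analysis plan cannot repair it: the data would not have been collected.

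**Working it through.** **Plan's own figure.** None exists for OS. The only power statement (about 75%, Section 11.3) concerns PFS-6 and has no bearing here.

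**Inputs from the protocol.** Survival contact stops 12 months after progression. Accrual takes 12 months with 12 months more follow-up, so potential follow-up is uniform on 12 to 24 months. n = 20. The reference figures for POM with low-dose DEX (Section 3.5.5) are median PFS 4.0 months and median OS 12.7 months.

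**Assumptions not in the protocol.** PFS is exponential. The share of PFS events that are deaths is 15% (range 0 to 50%). The shape of post-progression survival is varied, and each scenario is scaled to a true median OS of 12.7 months.

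**Step 1: when the cap acts.** Progression occurs after Day 1, so the cap falls later than month 12. A first-enrolled patient who progresses at month 4 has about 24 months of potential follow-up, but contact ends at 4 + 12 = 16.

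**Step 2: how many it affects.** Let λ = ln 2 / 4.0 = 0.1733 and let mean post-progression survival be 12.12 months. The share alive and inside the window when contact stops is

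0.85 × exp(−12/12.12) × [1 − (1 − e^(−12λ))/(12λ)] = 0.85 × 0.3715 × 0.579 = 0.183,

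or about 3.7 of 20 patients. Without a calendar cut-off it would be 0.85 × 0.3715 = 0.316. With 50% of PFS events being deaths (mean post-progression survival 64.28 months) it is 0.5 × 0.830 × 0.579 = 0.240. Seven further scenarios, with and without shared frailty, gave 11% to 21%.

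**Step 3: bias.** Kaplan-Meier with censoring at progression + 12 months, against the true OS curve (300,000 simulated patients per scenario):

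| Scenario | 18 months: KM vs true | 24 months: KM vs true |
|---|---|---|
| Constant post-progression hazard, 15% deaths (base) | 34.7 vs 34.0 (+0.7) | 22.8 vs 21.3 (+1.5) |
| Same, 0% deaths | 32.6 vs 31.5 (+1.1) | 20.1 vs 18.0 (+2.1) |
| Same, 30% deaths | 37.2 vs 37.1 (+0.1) | 26.7 vs 26.5 (+0.2) |
| Same, 50% deaths | 41.9 vs 43.5 (−1.6) | 34.5 vs 38.5 (−4.0) |
| Longer PFS goes with longer post-progression survival | 39.7 vs 37.7 (+2.0) | 32.6 vs 28.0 (+4.6) |
| Rising hazard (Weibull shape 1.5) | 31.7 vs 29.1 (+2.6) | 18.7 vs 13.8 (+4.9) |
| Falling hazard (shape 0.6) | 37.7 vs 38.6 (−0.9) | 27.4 vs 29.8 (−2.4) |
| Falling hazard (shape 0.4) | 39.5 vs 41.0 (−1.5) | 30.3 vs 34.6 (−4.3) |

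OS at 6 and 12 months is identical in every row, and the median stays at 12.69 to 12.71 months.

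**Step 4: why the sign changes.** The patients removed are at least 12 months past progression; those kept have progressed more recently or not at all. With constant hazards the monthly death hazard before progression is share × λ, and after progression it is 1/mean:

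- 15% deaths: 0.026 vs 1/12.12 = 0.083, so the bias is upward.
- 30% deaths: 0.052 vs 1/17.51 = 0.057, so it is nearly zero.
- 50% deaths: 0.087 vs 1/64.28 = 0.016, so it is downward.

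**Step 5: new therapy without progression.** This gap can act before month 12. If about 10% of patients are lost at the switch, KM minus true OS at 12 months is +2.3 points when their later death hazard is doubled, −0.4 when unchanged and −2.3 when halved.

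**Step 6: precision.** In the base case a common cut-off leaves about 20 × 0.34 × 0.5 = 3.4 patients at risk at 18 months. Under the rule about 1.9 remain. The standard deviation of the 18-month estimate with n = 20 is about 13 to 14 points under the rule and about 12 under a common cut-off. At 23.5 months fewer than one patient is expected at risk either way.

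**The case against.** The strongest reply is that nothing turns on OS. It is a descriptive secondary endpoint without a hypothesis or target. The 12.7-month figure is background, and no comparison with it is planned. With 20 patients, sampling error far exceeds the bias, and the 24-month differences sit where almost nobody would be at risk. All of this stands, and it limits the weight of the point. It does not defend the rule, which gives up late deaths for no stated gain.

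Three stronger readings are tempting but not supported:

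- **OS is biased upward.** The direction depends on hazard shapes and on the share of PFS events that are deaths, neither of which the protocol gives. Reasonable choices give zero or the opposite sign.
- **OS around the 12.7-month median is overstated.** The cap cannot act before month 12, and the median did not move in any scenario calibrated to 12.7. It can move if true OS is longer: with shared frailty, median PFS 4.0 and post-progression survival 8.0 months, the true median of 17.0 is estimated as 17.9.
- **Deaths after stopping for toxicity, including run-in DLT, are lost.** Section 7.9.1 lists toxicity, including DLT, as a reason for stopping SL-401. Section 7.9.2 follows patients who stop without progression monthly, then for survival, and names only withdrawal of consent as ending data collection. The clear gap is therefore new therapy before progression. For run-in DLT the documents conflict; they do not clearly drop these patients.

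It is also fair to say that 12 months after the last patient is a premise of the power statement, not an existing cut-off rule. Section 6.4 defines Study Completion differently.

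**Conclusion.** The point holds in limited form. The follow-up rule, stated consistently in five places, ties OS censoring to progression and to new therapy, inside the window that Section 11.3 assumes. Kaplan-Meier OS after month 12 may therefore be biased: upward if early progressors keep a higher death hazard, near zero or downward under other plausible assumptions. At 18 months the range found was −1.6 to +2.6 points, which is small against sampling error. These sizes rest on the assumed PFS and post-progression distributions and on uniform accrual. The share of patients who will switch therapy before progression is unknown.

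The change is worth making because it is cheap and recovers scarce late information. No conclusion of the trial is shown to be wrong without it.

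**What to change.** In the synopsis and Sections 6.4, 7.9.2 and 9.7 and in Table 13 footnote w, replace the survival rule with one sentence: every treated patient is contacted for survival every 3 months (telephone allowed, as in Section 9.7) from end of treatment until death, withdrawal of consent or a common study cut-off date, regardless of progression or new therapy. Delete the one-year cap and the dangling whichever-comes-first phrase. Name the cut-off, for example 12 months after the last patient is enrolled, and align it with Study Completion in Section 6.4.

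Reconcile the statement that run-in DLT patients leave the study (synopsis, Section 6.2.1) with Sections 7.9.1 and 7.9.2, so that their survival follow-up continues. This concerns data collection only and leaves the treatment rules as they are.

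Cost: a few telephone contacts. For the patient in Step 1 it is 24 − 16 = 8 months, or two to three calls. Protocol and consent wording also change. With only a common cut-off left, censoring is administrative and Kaplan-Meier estimates the true curve; in the frailty and no-frailty simulations it was within 0.2 points throughout.

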3.1 Multiple Myeloma

Multiple myeloma (MM) is a heterogeneous clonal B-cell malignancy characterized by the accumulation of abnormal antibody producing plasma cells in the bone marrow (BM). The disease is associated with a variety of clinical manifestations including lytic bone lesions, hypercalcemia, renal impairment and anemia. MM is the second most common hematologic malignancy and accounts for approximately 11,000 deaths per year in the United States and 19,000 in Europe (ACS 2013).

Current treatment strategies include the use of immunomodulatory drugs such as thalidomide and its derivatives, proteasome inhibitors such as bortezomib, synthetic corticosteroids, alkylating agents such as melphalan, anthracyclines, and autologous stem cell transplant. Despite recent therapeutic advances and the use of "novel agents", MM remains an incurable disease with a median survival of approximately 5 - 7 years (Kumar 2008).

The molecular mechanism by which MM cells evade drug-induced cytotoxicity and acquire drug resistant phenotypes include interaction of MM cells with the BM microenvironment which is composed of extracellular matrix (ECM) proteins such as fibronectin, collagen, and laminin, along with cellular elements such as hematopoietic stem cells, immune cells, BM endothelial cells, and bone marrow stromal cells (BMSCs). Adhesion of MM cells to ECM proteins and accessory cells leads to increased expression of factors such as IL-6, insulin-like growth factor (IGF-1), and vascular endothelial growth factor (VEGF), which in turn further stimulates growth and survival of the malignant clone (Chauhan 1996; Agarwal 2013).

In addition, early studies using both *in vitro* and *in vivo* MM models, have demonstrated increased numbers of pDCs in the BM microenvironent, which promotes MM cell growth and survival (Chauhan et al. 2009). These studies also showed increased interleukin-3 (IL-3) levels resulting from plasmacytoid dendritic cells (pDC) and MM cell interaction, which in turn, trigger MM cell growth and pDC survival.

3.2 Targeting Cancer Stem Cells

The field of cancer stem cells (CSCs) is a new area of cancer biology that may fundamentally alter the approach to oncology drug development. CSCs have been identified in virtually all major tumor types, including leukemia and cancers of the brain, breast, colon, prostate, and pancreas (Jordan et al. 2006). CSCs are the highly malignant "seeds" of a tumor that self-renew and generate more mature cells that comprise the bulk of the tumor, or "the tumor bulk." As such, CSCs appear to be responsible for tumor initiation, propagation, and metastasis. Many of the characteristics of CSCs, such as their slow growth, anti-cell death mechanisms, and presence of multi-drug resistance proteins, may enable CSCs to resist therapeutic agents traditionally used to treat cancer. This may be due to the many challenging characteristics of CSCs, including slow growth, presence of multi-drug resistance proteins, anti-cell death mechanisms, and increased

activity of cellular mechanisms that repair damaged deoxyribonucleic acid. CSCs are particularly resistant to chemotherapy, radiation, or targeted therapy relative to tumor bulk.

CSCs have also been shown to increase, as a percentage of total tumor cells, as a result of exposure to a traditional therapy (Bao et al. 2006; Hermann et al. 2008). Consistent with their pivotal role in the development of tumors and relapse, higher amounts of CSCs in patient tumors as a percentage of their entire cancer appear to correlate with poor prognosis. CSC fractions greater than 3.5% and 1% of the entire cancer correlate with poor survival outcomes in patients with acute myeloid leukemia (AML) and brain cancer, respectively (van Rhenen et al. 2005; Zeppernick et al. 2008).

